- Patients who were new users of Spiriva Respimat, or LTRA, or patients who were prescribed a higher dose of ICS/LABA FDC, or patients who switched to a new ICS/LABA FDC from the previous ICS/LABA FDC

Exclusion criteria:

- Patients who were prescribed other LAMA any time before or on the index date
- In the primary analysis, patients who were diagnosed with COPD before or on the index date will be excluded from the study.

(In this study, a COPD diagnosis is defined as at least one Readcode for COPD before or on the index date. Please refer to [annex 4](#) for the detailed medcodes for COPD and the related readterms)

Protocol for non-interventional studies based on existing data

BI Study Number 0205-0537

c25002535-01

 Proprietary confidential information © 2018 Boehringer Ingelheim International GmbH or one or more of its affiliated companies

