In addition, the following CPRD-linked data will be used in this study:

- Hospital Episode Statistics (HES) Admitted Patient Care (HES APC) data
- HES Accident and Emergency (HES A&E) data
- Patient Level Index of Multiple Deprivation

HES APC data are collected on all admissions to National Health Service (NHS) hospitals in England. HES APC also covers admissions to independent sector providers (private or charitable hospitals) paid for by the NHS. HES APC does not cover accident and emergency (A&E, emergency department) attendances or outpatient bookings. In the financial year 2014/15 (April to March), 18,731,987 hospital episodes from 451 different NHS hospital trusts (known as ‘providers’) were recorded in HES APC. HES APC provides detailed clinical, demographic and organizational information for each Finished Consultant Episode. Data on drugs prescribed through hospital pharmacies to inpatients are not available in HES APC [[R18-0523](#)]. In this study, HES APC will be used to assess hospitalization (all-cause, respiratory disease related, or asthma or lower respiratory condition related) in the year prior to the index date among patients who were treated at English NHS health care providers. HES A&E data consist of individual records of patient care administered in the accident and emergency setting in England. These data are a subset of national A&E data collected by NHS England to monitor the national standard that 95% of patients attending A&E should wait no longer than 4 hours from arrival to admission, transfer or discharge. A&E data are submitted by A&E providers of all types in England. Data collected includes details about patients’ attendance, outcomes of attendance, waiting times, referral source, A&E diagnosis, A&E treatment (drugs prescribed not recorded), A&E investigations and Health Resource Group [[R18-0524](#)]. In this study, HES A&E will be used to ascertain A&E attendance for asthma or low respiratory conditions, which will be used to calculate the number of asthma exacerbation in the year prior to the index date.

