9.9 LIMITATIONS OF THE RESEARCH METHODS

The main analysis will exclude patients with other respiratory disease (e.g., COPD). This will exclude asthma-COPD overlap patients and some other patients and the results may not be representative to all asthma patients. However, Spiriva has both asthma and COPD indications. Therefore, for asthma-COPD overlap patients, the reason for initiating Spiriva Respimat can be unclear in existing data. Since the primary objective is to describe the characteristics of asthma patients prior to the initiation of Spiriva Respimat for the treatment of Asthma, it would be reasonable to exclude asthma-COPD overlap patients,

This study is based on existing data. It is possible that misclassification may happen for the measurement of comorbidities. However, we will use all the available data before the index date to minimize the possibility of misclassification.

Some covariates such as smoking status, alcohol use, BMI, pulmonary function, and eosinophil count may not be well recorded in CPRD. In the analyses we will present missing data as a separate category.

Some information may be recorded very infrequently or not at all in CPRD, e.g., number of people in a household, over-the-counter medication use, prescriptions in secondary care. These variables will not be assessed in this study.

The CPRD only includes patient data captured from general practitioners. Although some information about patient contacts with secondary care could be manually entered into the patient record, details about these specialty visits and hospital admissions (including dates, diagnoses, tests performed, length of stay) may be incomplete.

The CPRD may not be representative of all practices in the UK based on geography and size. There are certain patient groups that are missing from primary care records, such as prisoners, private patients, some residential homes and the homeless. Thus, selection bias cannot be ruled out. However, studies suggested that CPRD patients are broadly representative of the UK population in terms of age and sex. Patients are also comparable to the UK census in

terms of ethnicity, and comparable to the Health Survey for England for body mass index distribution in most patient subgroups.

The HES APC data and HES A&E data only have data for patients from England.

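### The COPD exclusion rests on a GP Read-code list with no exacerbation or admission term, so some patients with hospital-recorded COPD can stay in the main analysis although linked hospital data are obtained

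*Protocol*

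**What the plan says.** Section 9.2 sets the rule: "In the primary analysis, patients who were diagnosed with COPD before or on the index date will be excluded from the study". The operational definition follows: "a COPD diagnosis is defined as at least one Readcode for COPD before or on the index date", with the codes in Annex 4. No hospital source is named.

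Section 9.9 gives the reason. Spiriva is indicated in both diseases, and "for asthma-COPD overlap patients, the reason for initiating Spiriva Respimat can be unclear in existing data". The exclusion therefore protects the primary objective, which concerns Spiriva started for asthma.

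Section 9.9 also says of the GP record that "details about these specialty visits and hospital admissions (including dates, diagnoses, tests performed, length of stay) may be incomplete".

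Section 9.4 lists linked "Hospital Episode Statistics (HES) Admitted Patient Care (HES APC) data" among the sources and states that "HES APC provides detailed clinical, demographic and organizational information for each Finished Consultant Episode". Its planned use is limited to admissions in the year before the index date: "HES APC will be used to assess hospitalization (all-cause, respiratory disease related, or asthma or lower respiratory condition related"). HES A&E, also obtained, carries an A&E diagnosis. Neither source enters the COPD definition.

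**The concern.** The exclusion separates asthma use of Spiriva from COPD use, yet it relies only on the record that the protocol describes as possibly incomplete for hospital diagnoses. Take a patient admitted with COPD whose GP record holds an asthma code but no Annex 4 code. Under the rule exactly as written, this patient is kept. The admission could even be counted as a respiratory hospitalization from HES APC while the patient is analysed as free of COPD.

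What is at stake is the description of the Spiriva group, including the primary outcome (arrhythmia), and the comparisons with the other groups. If retained COPD patients are older, smoke more and have more cardiac disease (a plausible assumption, not a statement of the protocol), the profile shifts towards COPD. If there are more of them in the Spiriva group, part of a difference could be read as channeling within asthma. Section 7 adds that the results may inform the choice of propensity-score variables in later studies.

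**Working it through.** **Code lists side by side.** Annex 4 covers diagnosis, severity grade, monitoring, annual review, follow-up, recall letters, emphysema and irreversible obstruction. It contains no term for a COPD exacerbation and none for a COPD admission. Annex 3 has both kinds for asthma (medcodes 185 and 7058), and the heart failure list in 9.3.2.2 has an emergency admission term (medcode 32898). The gap is specific to COPD.

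**The plan's own figures.** The protocol gives no rate of missed COPD, so there is no stated figure for this point to reproduce. Its only calculation is Table 1 in 9.5. A Wilson 95% interval reproduces 19 of its 20 cells; the other (n = 2,000, 10%) gives an upper limit of 11.4 against the stated 11.3. The same method is used below.

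**Inputs from the protocol.** Spiriva group n = 935 (9.5). A meaningful difference is an ASD of at least 10% (9.7.1).

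**Assumed inputs, with no source in the protocol.**
- Share of retained patients with unrecognised COPD: f in the Spiriva group, g in the comparator.
- Arrhythmia: 10% with COPD, 3% without.
- Ever-smoking: 90% with COPD, 50% without.

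**Formulas.** Observed prevalence is p = p0 + f × (pC − p0), where p0 is the prevalence without COPD and pC with it. For groups 1 and 2, with q = 1 − p, ASD = |p1 − p2| / √[(p1q1 + p2q2)/2].

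**Arrhythmia, g = 0.**
- f = 5% (about 47 of 935): 0.03 + 0.05 × 0.07 = 0.0335. ASD = 0.0035/0.1753 = 2.0 points.
- f = 15% (about 140 of 935): 0.03 + 0.15 × 0.07 = 0.0405. ASD = 0.0105/0.1843 = 5.7 points.

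**Ever-smoking, g = 0.**
- f = 10%: 0.50 + 0.10 × 0.40 = 0.54. ASD = 0.04/0.4992 = 8.0 points.
- f = 12.5%: 0.55 against 0.50. ASD = 10.0 points, at the cut-off.
- f = 15%: 0.56 against 0.50. ASD = 12.0 points.

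**Effect of g.** For smoking with f = 10% and g = 5%: 0.54 against 0.52, ASD = 0.02/0.4990 = 4.0 points. With f = g the spurious ASD is zero.

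**A second set of assumptions.** For a comorbidity at 5% without COPD and 15–20% with it, the ASD is 0.9–1.4 points at 2% versus 0%, 4.4–6.4 at 10% versus 0%, and 7.5–10.9 at 20% versus 2%.

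**Against sampling error.** The Wilson 95% interval around 3% at n = 935 is about 2.1–4.3%. The shifted arrhythmia values, 3.35% and 4.05%, lie inside it.

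**The case against.** The strongest reply is that the pathway is narrow. The index Spiriva prescription is issued by a GP, since 9.9 says secondary-care prescriptions are not assessed. For a leak, the GP must prescribe Spiriva while the record holds no Annex 4 code at any time up to and including the index date, and one code of any kind excludes the patient. Section 9.4 notes that hospital diagnoses and discharge data may be entered by the practice. Users of another LAMA are excluded, Spiriva initiators must be tiotropium-naive, and everyone needs an asthma code and a recent ICS/LABA FDC prescription. This stands as mitigation, but it does not remove patients whose first LAMA is Spiriva Respimat, who are the study group.

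A second reply is that one Read-code rule for the whole UK is defensible. HES covers England only, so using it for primary eligibility would apply different criteria by linkage status. This stands, and it determines where HES belongs in the fix.

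A third is that 9.9 already discloses incomplete hospital diagnoses and possible misclassification, and that age, smoking and respiratory admissions are tabulated by group. That is only partly an answer: 9.9 never mentions COPD patients missed by the definition, and a COPD-like profile in a table does not show whether it comes from missed COPD or from asthma patients.

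A reader might go further and infer that missed COPD sits mainly in the Spiriva group and would produce false channeling signals. The documents do not support this. They give no misclassification rate for any group, all four groups face the same asthma, ICS/LABA and COPD criteria, and a leak of zero in the comparator is the extreme case.

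**Conclusion.** The point holds as a weakness in a stated definition. Followed exactly, section 9.2 with Annex 4 can keep patients with hospital-recorded COPD in an analysis meant to describe asthma use, although data that could reveal some of them are already obtained. It is neither an arithmetic error nor a contradiction between sections.

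Its size is unknown. Under the assumed 5–15% leak for arrhythmia and 10% for smoking, with none in the comparator, the spurious ASD is about 2–8 points, short of the 10% cut-off. The cut-off is reached only with a larger and strongly one-sided leak, such as 12.5% versus 0% for smoking. For the descriptive objective, the assumed arrhythmia prevalence would be overstated by 12–35% in relative terms (3.35/3.0 and 4.05/3.0). Over-representation in the Spiriva group is a reasonable inference from the dual indication, but it remains an assumption.

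**What to change.** 1. Add COPD exacerbation and COPD admission Read terms to Annex 4 and apply the extended list to all patients in all four groups. Keep this single Read-code rule for the primary analysis.
2. In the HES-linked (England) subset, report by treatment group how many retained patients have a COPD or emphysema diagnosis in any HES APC episode before or on the index date.
3. Repeat the main tables in that subset without those patients, as a sensitivity analysis.
4. Add to 9.9 that the Read-code definition may miss hospital-recorded COPD, and that its distribution across groups is unknown outside the linked subset.

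The count in step 2 replaces the assumed leak with an observed figure for linked patients. The cost is a longer code list, one filter on data already requested, slightly fewer than 935 Spiriva patients and one additional set of tables. Unlinked patients outside England benefit only from step 1.

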9.3 VARIABLES

All the variables will be identified based on data recorded on the index date (date of dispensing/initiation of the exposure), or when a characteristic was not recorded on the index date, during the pre-index period (the one closest to the index date), unless otherwise specified.

9.3.1 Exposures

The study drug of interest is Spiriva Respimat. The exposure in the Spiriva group will be initiation of Spiriva Respimat. The exposure in the comparator group will include: 1) initiation of LTRA; 2) an increase in daily dose of ICS/LABA FDC; and 3) switching to a new ICS/LABA FDC.

To make sure that patients who initiated Spiriva Respimat or LTRA are new users of these drugs, patients who initiated Spiriva Respimat must have no exposure to tiotropium before the index date, and patients who initiated LTRA must have no exposure to LTRA before the index date.

An increase in daily dose of ICS/LABA FDC refers to any increase in the daily dose. If there was more than 1 dose increase during the study period, only the first dose increase will be included in the analysis.

Switching to a new ICS/LABA FDC refers to patients who switched to a new ICS/LABA FDC with different drug ingredient that was not prescribed during the pre-index period. If there was more than 1 switch during the study period, only the first switch will be used in the analysis.

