7. RATIONALE AND BACKGROUND

Asthma is a respiratory condition that causes symptoms of wheezing, shortness of breath, chest tightness and cough [[P18-03927](#)]. According to treatment guidelines, asthma patients at treatment step 3 and above should be treated with inhaled corticosteroids often in combination with long-acting beta agonists. However, many patients continue to have symptoms despite the use of these agents [[P10-08936](#)].

In late 2014, Spiriva Respimat (tiotropium), a long acting anticholinergic, was approved for treatment of asthma in the UK. Since this time, it has been approved for use in asthma patients in other countries including Japan and the United States. In the U.K., Spiriva® Respimat® is indicated as an add-on maintenance bronchodilator treatment in adult patients with asthma who are currently treated with the maintenance combination of inhaled corticosteroids ($\geq 800\mu\text{g}$ budesonide/day or equivalent) and long-acting beta2-agonists and who experienced one or more severe exacerbations in the previous year.

The current BTS/SIGN Guideline for the management of asthma recommends tiotropium by soft-mist inhaler as an alternate controller therapy at steps three, four and five of the asthma treatment paradigm, on top of inhaled corticosteroid (ICS)/LABA [[P18-03927](#)]. Alternatively, these patients could also be treated with a higher dose of ICS or ICS/LABA or MART, addition of leukotriene receptor antagonist (LTRA), addition of theophylline, beta agonist tablet, or switching to a different ICS/LABA, as shown in [figure 1](#).

Protocol for non-interventional studies based on existing data

BI Study Number 0205-0537

c25002535-01

Proprietary confidential information © 2018 Boehringer Ingelheim International GmbH or one or more of its affiliated companies

[figure not shown]

Figure 1 Summary of asthma management in adults.

Tiotropium is the first of its class approved for the use in the treatment of asthma. After a drug is launched in the market, it is important to identify patient clinical and socio-demographic characteristics of patients who initiate this treatment as opposed to other available treatments for patients at the same stage of disease. This type of study will allow us to evaluate potential channeling of prescribing to different patient populations. The results of the current study can also be used to determine the variables included in the calculation of propensity scores in future studies.

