- Allergic rhinitis
- Sinusitis
- Charlson comorbidity index [[R08-1584](#)]
- Cataract
- Osteoporosis
- Obesity

Concomitant prescriptions

- Asthma-related prescriptions in the year prior to index date
 - Short-acting beta agonists
 - Inhaled long-acting beta agonists (on top of ICS/LABA FDC)
 - Inhaled corticosteroid (ICS) (on top of ICS/LABA FDC)
 - Oral corticosteroid
 - Theophylline
 - Leukotriene Receptor Antagonist (LTRA)
 - Azithromycin,
 - Mucolytics
- Cardiovascular medications
 - Cardiac Glycosides
 - Thiazides
 - Loop diuretics
 - Antiarrhythmics
 - Beta blocker
 - Vasodilator Antihypertensive Drug
 - Centrally Acting Antihypertensive Drugs
 - Alpha-adrenoceptor Blocking Drugs
 - Drugs affecting the renin-angiotensin system

- Angiotensin Converting Enzyme Inhibitors
- Angiotensin II receptor blockers
- Renin Inhibitors
- Other antihypertensives
- Nitrates
- Calcium channel blockers
- Oral anticoagulants
- Heparin and other low molecular weight heparins
- Aspirin
- Antiplatelet
- Lipid-regulating Drugs
 - Bile Acid Sequestrants (lipid-regulating Drugs) - including Colesevelam
 - Ezetimibe (only in combination with Statin)
 - Fibrates
 - Statins
 - Nicotinic Acid Group
 - Omega-3 Fatty Acid Compounds
 - Other lipid-regulating drugs
- Glucose-lowering agents
- Non-steroidal anti-inflammatory drugs
- Psycholeptics
- Antipsychotics
- Antidepressants
- Agents for dementia

For concomitant medications used for diseases other than asthma the look-back time period will be limited to 180 days prior to the index date to increase the likelihood that the medications were used concomitantly. Concomitant medications will be categorized as current use (up to and including 60 days before index date) and past use (use any time prior to the 60 days before index date).

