9.7.1 Main analysis

The primary objective of this study is to describe the clinical and socio-demographic characteristics of asthma patients prior to the initiation of Spiriva Respimat for the treatment of Asthma. For this objective, patient baseline characteristics (as described in the “outcomes” and “covariates” section) will be tabulated and summarized for all new users of Spiriva Respimat. Means, standard deviations, medians, minimum, maximum, and interquartile range

(IQR) will be used to present continuous variables, counts and percentages will be used to present categorical variables.

The secondary objective of this study is to describe and compare the characteristics of asthma patients who initiated Spiriva Respimat to asthma patients who initiated a higher dose of ICS/LABA FDC, or LTRA, or alternatively those who switched from the previous ICS/LABA FDC to a new ICS/LABA FDC. For this objective, patient characteristics (as described in the “outcomes” and “covariates” section) will be tabulated for the patients that initiated or switched to the other available treatments separately, using measures as described for the patient baseline characteristics of Spiriva.

Patient characteristics (as described in the “outcomes” and “covariates” section) will be compared among patients who initiated Spiriva Respimat and patients in other treatment groups. Analyses will be conducted in unmatched cohorts and differences between spiriva restinmat and each of the other exposure groups will be assessed using absolute standardized differences (ASD), where an ASD of at least 10% will be considered a meaningful difference [[R16-1227](#)].

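### In the Spiriva-LTRA contrast, prior-year LTRA use is zero by eligibility in the LTRA group, yet it is compared under the 10% ASD rule with no exception

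*Protocol*

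**What the plan says.** Protocol section 9.3.1 (Exposures) sets a separate new-user rule for each drug. For the comparator, "patients who initiated LTRA must have no exposure to LTRA before the index date". For the study drug, "patients who initiated Spiriva Respimat must have no exposure to tiotropium before the index date". Nothing in sections 9.2 or 9.3.1 restricts earlier LTRA use among Spiriva starters. The LAMA exclusion in section 9.2 applies to all groups; the LTRA-naive rule applies to the LTRA group alone.

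Section 9.3.3 (Covariates) has a block headed "Asthma-related prescriptions in the year prior to index date", and LTRA is one of its items.

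Under section 9.7.1 (Main analysis), all characteristics from the outcome and covariate sections "will be compared among patients who initiated Spiriva Respimat and patients in other treatment groups". The cohorts are unmatched, each comparator is taken in turn, and the reading rule is that "an ASD of at least 10% will be considered a meaningful difference". No covariate is exempted for any contrast.

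Section 7 gives the purpose: to see whether prescribing is channeled to different patients than those given other treatments at a comparable stage of disease. It adds that the results "can also be used to determine the variables included in the calculation of propensity scores in future studies".

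**The concern.** The one-year covariate window lies wholly inside the period in which LTRA starters must be LTRA-free. Their value on this row is fixed before any data are seen, while the Spiriva value is free to vary. Any prior use among Spiriva starters then counts in full towards the ASD, and the 10% rule would label the result meaningful.

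That label is not evidence about how prescribers choose between the two drugs. Suppose every LTRA-naive patient were allocated to Spiriva or LTRA at random. LTRA-experienced patients could still enter only the Spiriva group, so the row could be flagged with no channeling at all among patients eligible for both groups.

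The same asymmetry can reach other rows. Spiriva starters who have already had an LTRA may differ in exacerbations, oral corticosteroid use or symptom score, and the LTRA group has no counterpart to them. Part of any difference on those rows could come from the entry rule, and the planned table would not show how much.

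**Working it through.** **The protocol's own figures.** The protocol states no ASD value. Its only computed figures are the confidence intervals in Table 1 (section 9.5). Wilson score intervals reproduce 19 of the 20 cells; the exception is 2,000 users at 10%, where the computed upper limit is 11.4 and 11.3 is printed, a rounding matter. Table 1 is not at issue here.

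**Inputs**
- LTRA group, LTRA in the prior year: 0% (sections 9.3.1 and 9.3.3).
- Spiriva group, LTRA in the prior year: *p*, not given in the protocol and therefore varied.
- Spiriva group size: 935 (feasibility count, section 9.5).
- Threshold: ASD of at least 0.10 (section 9.7.1).
- Formula: the standard ASD for a binary variable, assumed because the protocol does not print one.

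**Formula.** ASD = |p1 − p2| / √{[p1(1 − p1) + p2(1 − p2)] / 2}. With p2 = 0 this becomes p / √{p(1 − p)/2} = √{2p/(1 − p)}.

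**Where the flag is crossed.** Setting √{2p/(1 − p)} = 0.10 gives 2p = 0.01(1 − p), so p = 0.01/2.01 = 0.4975%. In patients, 935 × 0.004975 = 4.65, so 5 are needed:
- 4 of 935: ASD 0.093, not flagged
- 5 of 935: ASD 0.104, flagged

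The chance of at least 5 prior users among 935 is 0.50 at a true prevalence of 0.5%, 0.956 at 1%, and about 1.0 at 2% or more.

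**ASD over an assumed range of prior use**

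| Prior LTRA in Spiriva group (assumed) | ASD against 0% |
|---|---|
| 0.1% | 0.045 |
| 0.5% | 0.100 |
| 1% | 0.142 |
| 5% | 0.324 |
| 10% | 0.471 |
| 20% | 0.707 |
| 30% | 0.926 |

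**Against an ordinary row.** If the comparator value were free and stood at 10%, the Spiriva value would have to reach 13.2% to be flagged. At 30% it would have to reach 34.7%. Against a fixed zero, 0.5% is enough.

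**Alternative reading.** Section 9.3 says variables are taken on the index date first, unless otherwise specified. If that were applied here and the index prescription counted, the LTRA group would be at 100%. The ASD becomes √{2(1 − p)/p}, or 4.24, 2.16 and 1.41 at *p* of 10%, 30% and 50%. The row is fixed by design under either reading.

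**The case against.** The study is descriptive and unmatched. The 10% label triggers no test, exclusion or adjustment, and a careful reader who sees 0% beside a stated new-user rule will understand why. How a cell is marked, or whether a sensitivity column is added, is often left to an analysis plan or programming specification. Who receives Spiriva is also the question being asked: if its starters have often had an LTRA already, that is a true feature of the group.

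Much of this stands. The Spiriva percentage is a genuine finding and should be kept; only the LTRA group's value is fixed. The display can be settled elsewhere. But the protocol itself fixes the entry rule, the covariate, the window and the threshold, and applies the threshold without exception. Followed as written, it labels a row determined by design as a meaningful difference.

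Three stronger readings are tempting and are not supported:
- *The contrast sets LTRA-experienced against LTRA-naive patients.* Spiriva starters are unrestricted on LTRA, so they may be a mix, in a proportion the protocol does not give.
- *Severity differences in this contrast are artefacts.* The entry rule may contribute to them, but nothing in the protocol allows the contribution to be estimated, and some of the difference may be real.
- *The study will carry a non-overlapping variable into later propensity scores.* Section 7 says only that the results may guide variable choice. It does not say that every flagged row is nominated, or that a later study would keep these entry rules.

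**Conclusion.** The point holds for the Spiriva-LTRA contrast only. The LTRA group's value for prior-year LTRA is zero by eligibility, and the 10% rule would flag the row once about 0.5% of Spiriva starters (5 of 935) had such use. That the flag will be raised is an assumption, since the protocol gives no prevalence, but only near-zero prior use avoids it. The ASDs of 0.47, 0.71 and 0.93 at 10%, 20% and 30% are illustrations. An effect of the entry rule on other rows is possible but unquantified. The primary description of Spiriva starters and the contrasts with the dose-increase and switch groups are unaffected, because prior LTRA use is not fixed by eligibility there.

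**What to change.** In section 9.7.1, for the Spiriva-LTRA contrast:

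1. Report the prior-LTRA percentage descriptively, mark it as determined by design, and do not read it against the 10% rule.
2. Add a sensitivity column of ASDs for all characteristics, with the Spiriva group restricted to patients who had no LTRA at any time before the index date. This is the window that section 9.3.1 applies to the LTRA group; a one-year restriction would not match it. Keep the full-group column beside it.
3. State that, if the results inform propensity scores in a study with the same entry rules, prior LTRA use has no overlap in this contrast.

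The cost is a sentence or two and one extra column. The downside is a smaller Spiriva group in that column. It would fall below the 500 that section 9.5 calls adequate only if LTRA use at any earlier time exceeds about 46.5% (1 − 500/935 = 0.465). The planned full-group comparison is not lost.
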